16.0 Data Handling Conventions

16.1 Visit Time Windows

Table 16.1-1 presents the visits assigned for safety analyses and the corresponding range of treatment days (window) during which an actual visit may occur.

Table 16.1-1. Visit Time Windows for Safety Analysis

Derived Visit	Scheduled Test / Visit Day^a	Window
Baseline	Day 1	Days \leq 1
Visit 4	Day 14	Days [2, 21]
Visit 5	Day 28	Days [22, 43]
Visit 6	Day 56	Days [44, 71]
Visit 7	Day 84	Days \geq 72
End of Study ^b	Final or termination visit during the double-blind Treatment Period	

a Relative to the date of the first dose; Day 1 = the day of the first dose.

b “End of Trial” will be presented in analysis tables for safety parameters, including clinical laboratory and vital signs.

If the visit date is on or after the date of the first dose of double-blind study treatment, the study day is calculated by visit date – date of the first dose of double-blind investigational product + 1. If the visit date is before the date of the first dose of double-blind investigational product, the study day is calculated by visit date – date of the first dose of double-blind investigational product. Therefore, a negative day indicates a day before the start of the double-blind investigational product.

If a participant has 2 or more visits within the same window, the last visit with a nonmissing value will be used for analysis.

16.2 Analysis Weeks and Visit Time Windows for Efficacy Analysis

16.2.1 Analysis Weeks for Efficacy Analysis

Table 16.2.1-1 below presents the analysis weeks assigned for the efficacy analysis of the participant daily diary data related to DGSSD. These analysis weeks will be used in the calculations for all week-based endpoints (eg, weekly DGSSS, weekly vomiting frequency, individual symptoms weekly scores etc.).

Table 16.2.1-1. Analysis Time Windows for Efficacy Analysis

Period	Analysis Week	Begins^a	Ends^a
Pretreatment (Baseline ^b)	Week -2	Day -14	Day -8
	Week -1	Day -7	Day -1
Treatment	Week 1	Day 1, day of randomization	Day 7
	Week 2	Day 8	Day 14
	Week 3	Day 15	Day 21
	Week 4	Day 22	Day 28
	Week 5	Day 29	Day 35
	Week 6	Day 36	Day 42
	Week 7	Day 43	Day 49
	Week 8	Day 50	Day 56
	Week 9	Day 57	Day 63
	Week 10	Day 64	Day 70
	Week 11	Day 71	Day 77
	Week 12	Day 78	Day 84

[figure not shown]
a Relative to the date of randomization; Day 1 = the day of randomization.

[figure not shown]
b Baseline values for efficacy parameters will be derived as average of the two pretreatment weeks.

[figure not shown]
For the Treatment Period, diary day is calculated as (diary date - date of randomization + 1). For the Pretreatment Period, diary day is calculated as (diary date - date of randomization).

16.2.2 Visit Windows for Efficacy Analysis

Visit windows as defined in Section 16.1 will be used for the analysis by visit

16.4 Repeated or Unscheduled Assessments of Safety Parameters

If a participant has repeated assessments before the start of double-blind treatment with investigational product, the results from the final assessment made before the date of the first dose will be used as baseline. If EOT assessments are repeated or unscheduled, the last postbaseline assessment will be used as the EOT assessment for generating summary statistics.

However, all postbaseline assessments will be used for PCS value determination, and all assessments will be presented in the data listings.

16.5 Missing Date of the Last Dose of Study Treatment

When the date of the last dose of the double-blind investigational product is missing, all efforts should be made to obtain the date from the Investigator. If it is still missing after all efforts have been made, the last diary date will be used as the last dose date.

16.6 Missing Severity Assessment for Adverse Events

If severity is missing for an AE that started before the date of the first dose of double-blind investigational product, an intensity of mild will be assigned. If severity is missing for an AE that started on or after the date of the first dose of double-blind investigational product, an intensity of severe will be assigned. The imputed values for severity assessment will be used for the incidence summary; the values will be shown as missing in the data listings.

16.7 Missing Causal Relationship to Study Treatment for Adverse Events

If the causal relationship to the investigational product is missing for an AE that started on or after the date of the first dose of double-blind investigational product, a causality of yes will be assigned. The imputed values for causal relationship to double-blind treatment will be used for the incidence summary; the values will be shown as missing in the data listings.

16.8 Missing Date Information for Adverse Events

The following imputation rules apply to cases in which the start date is incomplete (ie, partial missing) for AEs.

Missing day and month

- If the year is the same as the year of the date of the first dose of double-blind investigational product, then the day and month of the date of the first dose of double-blind investigational product will be assigned to the missing fields.
- If the year is prior to the year of the date of the first dose of double-blind investigational product, then December 31 will be assigned to the missing fields.
- If the year is after the year of the date of the first dose of double-blind investigational product, then January 1 will be assigned to the missing fields.

Missing month only

- The day will be treated as missing and both month and day will be replaced according to the above procedure.

Missing day only

- If the month and year are the same as the month and year of the date of the first dose of double-blind investigational product, then the date of the first dose of double-blind investigational product will be assigned to the missing day.
- If either the year is before the year of the date of the first dose of double-blind investigational product or if both years are the same but the month is before the month of the date of the first dose of double-blind investigational product, then the last day of the month will be assigned to the missing day.
- If either the year is after the year of the date of the first dose of double-blind investigational product or if both years are the same but the month is after the month of the date of the first dose of double-blind investigational product, then the first day of the month will be assigned to the missing day.

If the stop date is complete and the imputed start date as above is after the stop date, the start date will be imputed by the stop date.

If the start date is completely missing and the stop date is complete, then the following algorithm is used to impute the start date:

- If the stop date is on or after the date of the first dose of double-blind investigational product, the date of the first dose of double-blind investigational product will be assigned to the missing start date.
- If the stop date is before the date of the first dose of double-blind investigational product, the stop date will be assigned to the missing start date.

16.9 Missing Date Information for Prior or Concomitant Medications

For prior or concomitant medications, excluding rescue medications, incomplete (ie, partly missing) start dates and/or stop dates will be imputed. When the start date and the stop date are both incomplete for a participant, the start date will be imputed first.

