Prior medication is defined as any medication started before the date of the first dose of double-blind study treatment. *Concomitant medication* is defined as any medication taken on or after the date of the first dose of double-blind study treatment. Any prior medications started more than 30 days before the date of the first dose of double-blind study treatment and any concomitant medications started after the date of the last dose of double-blind study treatment will not be presented in the summary tables, but will be included in the participant data listings.

Both prior and concomitant medication use will be summarized by the number and proportion of participants in each treatment group for the Safety Population. The *WHO Drug Dictionary*, Version B2 March 2017 or newer, will be used to classify prior and concomitant medications by WHO Drug Anatomical/Therapeutic/Chemical category and drug preferred name. Multiple medications used by a participant will only be counted once for the coded drug preferred name or therapeutic class.

9.0

Extent of Exposure and Treatment Compliance

9.1

Extent of Exposure

Exposure to the study treatment for the Safety Population during the double-blind treatment period will be summarized for treatment duration, calculated from the eDiary as the number of days from the date of the first dose of study treatment to the date of the last dose of study treatment, inclusive. Descriptive statistics (number of participants, mean, SD, median, Q1, Q3, minimum, and maximum) will be presented by treatment group. The date of first dose is the date of randomization(date of baseline visit).

Patient-years, defined as duration of exposure to the study treatment in years, will be summarized by treatment for the Safety Population.

9.2

Measurement of Treatment Compliance

Dosing compliance for a specified period is defined as the number of injections actually taken by a participant during that period divided by the number of injections expected for the same period multiplied by 100. The number of injections actually taken is obtained from the participants' responses in the item of 'How many injections of study medication have you administered today?' from the electronic hand-held device. The number of injections expected during a period is the number of days in the period multiplied by 2.

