16.9.1 Incomplete Start Date

The following rules will be applied to impute the missing numeric fields for an incomplete prior or concomitant medication start date. If the stop date is complete (or imputed) and the imputed start date is after the stop date, the start date will be imputed using the stop date.

Missing month and day

- If the year of the incomplete start date is the same as the year of the first dose of study treatment, the month and day of the first dose of study treatment will be assigned to the missing fields
- If the year of the incomplete start date is before the year of the first dose of study treatment, *December 31* will be assigned to the missing fields
- If the year of the incomplete start date is after the year of the first dose of study treatment, *January 1* will be assigned to the missing fields

Missing month only

- If only the month is missing, the day will be treated as missing and both the month and the day will be replaced according to the above procedure

Missing day only

- If the month and year of the incomplete start date are the same as the month and year of the first dose of study treatment, the day of the first dose of study treatment will be assigned to the missing day

- If either the year of the incomplete start date is before the year of the date of the first dose of study treatment or if both years are the same but the month of the incomplete start date is before the month of the date of the first dose of study treatment, the last day of the month will be assigned to the missing day.
- If either the year of the incomplete start date is after the year of the date of the first dose of study treatment or if both years are the same but the month of the incomplete start date is after the month of the date of the first dose of study treatment, the first day of the month will be assigned to the missing day

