16.9.2 Incomplete Stop Date

The following rules will be applied to impute the missing numeric fields for an incomplete prior or concomitant medication stop date. If the date of the last dose of study treatment is missing, impute it as described in Section 16.4. If the imputed stop date is before the start date (imputed or nonimputed start date), the imputed stop date will be equal to the start date.

Missing month and day

- If the year of the incomplete stop date is the same as the year of the last dose of study treatment, the month and day of the last dose of study treatment will be assigned to the missing fields
- If the year of the incomplete stop date is before the year of the last dose of study treatment, *December 31* will be assigned to the missing fields
- If the year of the incomplete stop date is after the year of the last dose of study treatment, *January 1* will be assigned to the missing fields

Missing month only

- If only the month is missing, the day will be treated as missing and both the month and the day will be replaced according to the above procedure

Missing day only

- If the month and year of the incomplete stop date are the same as the month and year of the last dose of study treatment, the day of the last dose of study treatment will be assigned to the missing day
- If either the year of the incomplete stop date is before the year of the date of the last dose of study treatment or if both years are the same but the month of the incomplete stop date is before the month of the date of the last dose of study treatment, the last day of the month will be assigned to the missing day

- If either the year of the incomplete stop date is after the year of the date of the last dose of study treatment or if both years are the same but the month of the incomplete stop date is after the month of the date of the last dose of study treatment, the first day of the month will be assigned to the missing day.

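### SAP 16.9.1 and 16.9.2 repair the same partly dated medication record in opposite ways, and 16.8 has no cap on adverse event onset when the stop date is partial

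*SAP*

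**What the plan says.** SAP 16.9 sets the scope for medications: "For prior or concomitant medications, excluding rescue medications, incomplete (ie, partly missing) start dates and/or stop dates will be imputed". It then fixes the order: "When the start date and the stop date are both incomplete for a participant, the start date will be imputed first".

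SAP 16.9.1 deals with the start. If month and day are missing and the year is the first-dose year, "the month and day of the first dose of study treatment will be assigned to the missing fields". If only the day is missing and the month is before the first-dose month, "the last day of the month will be assigned to the missing day". A start with only its month missing is handled as if the day were missing too. The safeguard reads: "If the stop date is complete (or imputed) and the imputed start date is after the stop date", in which case the start is taken from the stop.

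SAP 16.9.2 deals with the stop, and its safeguard runs the other way, resetting the stop to the start. The rule opens: "If the imputed stop date is before the start date (imputed or nonimputed start date), the imputed stop date will be equal to".

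SAP 8.0 calls a drug prior if it began before the first double-blind dose. Concomitant medication "is defined as any medication taken on or after the date of the first dose of double-blind study treatment".

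SAP 16.8 gives adverse event onset dates the same year-only rule. Its safeguard is narrower: "If the stop date is complete and the imputed start date as above is after the stop date", the start becomes the stop. It sets no order of imputation and has no rule for a partly recorded stop. SAP 11.1 flags an event as treatment-emergent by its onset date relative to the first and last dose.

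**The concern.** There are two separate faults.

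- **Medications: a contradiction.** When both dates are partial, 16.9.1 lets the imputed stop win and 16.9.2 lets the imputed start win. Under the start-first order, no imputed stop exists when 16.9.1 is applied, so its clause about imputed stops has nothing to act on. Two programmers could each follow the text and classify the same drug differently. Following 16.9 and 16.9.2, an invented start date can override a recorded stop month.
- **Adverse events: a gap.** Protocol 9.2.1 collects events from consent, so events that end before first dose will be in the data. If such an event has a partial stop, nothing in 16.8 prevents the imputed onset from falling on the first-dose date.

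At stake is whether records show as before or on treatment in the medication and adverse event tables. An event that is misplaced in this way, and whose severity or causality is also missing, would by SAP 16.6 and 16.7 be counted as severe or related as well.

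**Working it through.** The plan states no figure on this point, so the check is to apply the rules literally to assumed dates.

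**Inputs (assumed).** First dose is 20 June 2019. Last dose is Day 84: 20 June + 83 days = 11 September 2019. The start is recorded as 2019 only and the stop as May 2019. The recorded stop month ends on 31 May, so the true stop is certainly before first dose.

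**Medication and adverse event, step by step**

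| Step | 16.9 order, then 16.9.2 | 16.9.1 clause on imputed stops honoured | Adverse event under 16.8 |
|---|---|---|---|
| Imputed start | 20 Jun 2019 | 20 Jun 2019 | 20 Jun 2019 |
| Imputed stop | 31 May 2019 | 31 May 2019 | no rule |
| Safeguard | stop moved to 20 Jun | start moved to 31 May | not triggered, stop incomplete |
| Result | 20 Jun to 20 Jun | 31 May to 31 May | onset 20 Jun |
| Label | concomitant, not prior | prior, not concomitant | treatment-emergent |

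**How far it reaches.** Start and stop can each be a full date, a month and year, or a year only: 3 × 3 = 9 combinations. All nine were enumerated with first doses on every fifth day of 2019 and last dose on Day 84, keeping only records whose recorded stop is certainly before first dose.

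- Misclassification occurs in one combination: year-only start with a month-and-year stop. The other eight give none.
- Within that combination it affects 28,019 of 31,325 date pairs when both dates lie within 42 days before first dose (4 weeks of Screening plus 2 of Run-in, 6 × 7 = 42). It affects 56,043 of 180,043 pairs when the window is 365 days. The counts are the same for medications (16.9 with 16.9.2) and adverse events. They are grid counts, not expected frequencies.
- The remaining pairs in that combination have a start in an earlier year. The start then goes to 31 December of that year and stays before first dose.
- With the 16.9.1 clause honoured, no enumerated medication record is misclassified.

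**Check on possible repairs.** Reversing the order outright fails on a mirror case with the same doses: start October 2019, stop 2019 only. The stop is imputed as 11 September and the start as 1 October. Capping the start at the imputed stop moves it to 11 September, against its recorded month. It also brings a drug begun after last dose into summary tables that SAP 8.0 says should omit it.

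Capping the start at the latest date compatible with the recorded stop avoids this:

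- Mirror case: the cap is 31 December 2019, so the start stays at 1 October. The stop is imputed as 11 September and reset to 1 October by 16.9.2.
- Main example: the cap is 31 May 2019, so the drug runs from 31 May to 31 May and is prior. The event's onset is no later than 31 May and is not treatment-emergent.

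**The case against.** The strongest reply is that this is rare and mostly already guarded. A complete stop date protects both drugs and events. A start with a known month before first dose stays there, and a year-only start in an earlier year goes to 31 December. Adverse event collection begins at consent, about six weeks at most before first dose, so a year-only onset with a known stop month should be unusual. Counting a doubtful event as treatment-emergent is also conservative, in line with the rules for missing severity and causality. Rescue medications lie outside 16.9. SAP 8.0 summarises medication use descriptively, so no test is affected. SAP 4.0 says the study ended early and only an abbreviated report is planned. The appendix that outlines its content is not in the text available, so the tables may not be produced.

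All of that limits the size, and it stands. It does not remove the contradiction between 16.9.1 and 16.9.2. The conservatism argument is weaker: in this pattern the recorded stop month leaves no doubt that the event ended before first dose, and 16.8 already lets a complete stop limit the onset.

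A reader might infer that any drug stopped before first dose is moved onto Day 1. The documents do not support that: it takes this one pattern, and applying 16.9.1 instead keeps the drug prior. A reader might also blame the start-first order for the adverse event problem. That order covers medications only; the cause is the narrow cap in 16.8.

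**Conclusion.** The point holds as a minor one. Sections 16.9.1 and 16.9.2 conflict and must be reconciled, and 16.8 needs a rule for partial stop dates. The error arises only if the start lacks its month, its year is the first-dose year, and the stop is a month and year before the first-dose month. Each such drug record then changes wholly from prior to concomitant if 16.9 and 16.9.2 are followed, and each such event becomes treatment-emergent.

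The number of records is probably small but cannot be estimated, because the documents give no rate for partial dates. The adverse event half assumes that the imputed onset drives the treatment-emergent flag; 16.8 would otherwise have little purpose. The effect is confined to descriptive tables, if they are still produced. No efficacy result changes.

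A reader might also infer that a washed-out prohibited drug would be reported as a protocol breach. The available text derives no deviations from imputed dates and defines no per-protocol population, so that is not supported.

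**What to change.** Keep the start-first order in 16.9. In both 16.8 and 16.9.1, state that an imputed start may not be later than the latest date compatible with the recorded parts of the stop date: the stop itself if complete, the last day of a recorded month, or 31 December of a recorded year. In 16.9.1 this replaces the condition that the stop be complete or imputed. The reset in 16.9.2 can then stay, because the start will already respect the recorded stop.

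In the same edit, correct the cross-reference in 16.9.2: it sends the reader to 16.4 for a missing last-dose date, but that rule is in 16.5.

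The cost is two or three sentences in the SAP and a small change to the date-imputation program, with the main example and the mirror case as test records.

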16.9.1 Incomplete Start Date

The following rules will be applied to impute the missing numeric fields for an incomplete prior or concomitant medication start date. If the stop date is complete (or imputed) and the imputed start date is after the stop date, the start date will be imputed using the stop date.

Missing month and day

- If the year of the incomplete start date is the same as the year of the first dose of study treatment, the month and day of the first dose of study treatment will be assigned to the missing fields
- If the year of the incomplete start date is before the year of the first dose of study treatment, *December 31* will be assigned to the missing fields
- If the year of the incomplete start date is after the year of the first dose of study treatment, *January 1* will be assigned to the missing fields

Missing month only

- If only the month is missing, the day will be treated as missing and both the month and the day will be replaced according to the above procedure

Missing day only

- If the month and year of the incomplete start date are the same as the month and year of the first dose of study treatment, the day of the first dose of study treatment will be assigned to the missing day

- If either the year of the incomplete start date is before the year of the date of the first dose of study treatment or if both years are the same but the month of the incomplete start date is before the month of the date of the first dose of study treatment, the last day of the month will be assigned to the missing day.
- If either the year of the incomplete start date is after the year of the date of the first dose of study treatment or if both years are the same but the month of the incomplete start date is after the month of the date of the first dose of study treatment, the first day of the month will be assigned to the missing day

